2.4.6.2 Deaths

A listing of all deaths during the study will be provided, including the period of occurrence (eg, pretreatment, on-treatment or post-treatment follow up) and the reason of death. A table summary for number (%) of patients who died by study period and reason of death might be generated as needed.

2.4.6.3 Analyses of laboratory variables

Hematological and clinical biochemistry toxicities will be assessed from laboratory test parameters defined in [Section 2.1.4.3](#). Each test result will be graded by NCI-CTCAE version 5.0 whenever applicable.

For hematological parameters and for some selected biochemistry parameters, Sanofi sponsor generic ranges (LLN, ULN) are defined and will be used for grading (see list of parameters in [Appendix F](#)). For other biochemistry parameters (eg, for hepatic enzymes ALT, AST, Alkaline phosphatase, total bilirubin), grading will be derived using local laboratory normal ranges. The number of patients with abnormal laboratory tests at baseline will be presented by grade and all grades together. The frequency of patients in each grade and all grades of laboratory abnormalities during treatment will be summarized. For patients with multiple occurrences of the same laboratory variable during the treatment, the maximum grade (worst) per patient will be used. The denominator used for percentage calculation is the number of patients with at least 1 evaluation of the laboratory test during the considered observation period. When appropriate, the summary table will present the frequency of patients with any grade of abnormal laboratory tests and with Grade 3-4 abnormal laboratory tests.

In addition, for hematology and biochemistry toxicities, shift tables showing the number of patients in each grade at baseline by grade during the on-treatment period will be provided.

For laboratory tests for which NCI-CTCAE V5.0 scale is not applicable, potentially clinically significant abnormalities (PCSA) values are defined as abnormal values considered medically important by the Sponsor according to predefined criteria/thresholds based on literature review ([Appendix H](#)).

PCSA criteria will determine which patients had at least 1 PCSA during the on-treatment period, taking into account all evaluations performed during the on-treatment period, including

nonscheduled or repeated evaluations. The incidence of PCSA any time during the on-treatment period will be summarized by treatment group irrespective of the baseline level.

Laboratory parameters for which both CTCAE grading or PCSA criteria are not applicable will be classified into low/normal/high group by means of laboratory normal ranges. For such parameters, a summary table which present the frequency of patients with any abnormal test will be provided.

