1.3 SCHEDULE OF ACTIVITIES (SOA)

Procedure ^a	Screening	Treatment Period (14 days)			Surgery ^c	Post treatment safety follow-up period	Notes
	up to 14 days before randomization	D1 ^b	D7 (±2)	D14	D15 (+1)	30 (±7) days after last IMP intake	
Informed consent	X						Informed consent (including genetic sampling) may be signed more than 14 days prior to randomization.
Inclusion and exclusion criteria	X						Recheck clinical status before randomization, and before 1st dosing of IMP if 1st dosing and randomization are not on the same day. See Section 5.1 and Section 5.2 for details.
Randomization	X						To take place once the consented participant has completed all the necessary screening procedures and is deemed eligible for study entry by the Investigator or designee and has already a breast conservative surgery scheduled per protocol timing requirement. All eligible participants must be randomized using IRT. Participants will be randomized within 3 days prior to first dosing of IMP. See Section 6.3 for details
Demography	X						Demography includes age, year of birth, gender, race, ethnicity.
Follicle stimulating hormone (FSH) test	X						Serial FSH measurements (at least 2) with at least 1-day interval between the measurements are required to confirm postmenopausal status for the patients who have received hormonal replacement therapy but have discontinued this treatment and in the absence of amenorrhea >12 months. FSH level in the postmenopausal range assessed prior to screening can be used as the first FSH measurement.
Full physical examination including height / weight / ECOG PS	X	(X)		X		X	Height will only be assessed at screening. Other assessments will be repeated within 1 day prior to the first dosing of IMP if abnormal or if screening assessment >7 days of D1. See Section 8.2.1 for details.
Past and current medical conditions	X						Including previous and ongoing medications, prior anticancer therapies, disease history.

Procedure ^a	Screening	Treatment Period (14 days)			Surgery ^c	Post treatment safety follow-up period	Notes
	up to 14 days before randomization	D1 ^b	D7 (±2)	D14	D15 (+1)	30 (±7) days after last IMP intake	
Laboratory assessments	X	(X)		X			Standard hematology, clinical chemistry and coagulation panels. These assessments will be repeated within 1 day prior to the first dosing of IMP if abnormal or if screening assessment >7 days of D1. See Section 10.2 for details.

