7.1 DISCONTINUATION OF STUDY INTERVENTION

7.1.1 Definitive discontinuation

The duration of study intervention is 14 days. Participants may withdraw from study treatment if they decide to do so, at any time and irrespective of the reason, or this may be done at the discretion of the Investigator. All efforts should be made to document the reason(s) for discontinuation and this should be documented in the eCRF. If study intervention is permanently discontinued, the participant will remain in the study to be evaluated for safety.

Handling of participants after definitive intervention discontinuation

If the participants withdraw from study treatment before completing 14-day period, they will be requested to get back to the study sites as per planned visit dates after discontinuation. As an example, a participant who discontinues treatment on Day 6 will come to site for planned visits on Day 7 and Day 14. All procedures pre-scheduled for these Day 7 and Day 14 visits will be performed except PK sampling and ECG. If the participants have received less than 70% of planned dose (ie, less than a total of 10 days of treatment), the breast ultrasound will not be performed either. The post-treatment core-cut biopsy sampling from surgery specimen or a new core-cut biopsy will be performed as scheduled.

All participants will be requested to participate in the post-treatment safety follow-up visit (30 [\pm 7] days after last IMP intake).

Participants will be followed-up according to the study procedures specified in this protocol up to the scheduled date of study completion, or up to recovery or stabilization of any AE to be followed-up as specified in this protocol, whichever comes last.

All cases of definitive intervention discontinuation must be recorded by the Investigator in the appropriate pages of the e-CRF when considered as confirmed.

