8.3 ADVERSE EVENTS AND SERIOUS ADVERSE EVENTS

Adverse event of special interest

An adverse event of special interest (AESI) is an AE (serious or nonserious) of scientific and medical concern specific to the Sponsor's product or program, for which ongoing monitoring and immediate notification by the Investigator to the Sponsor is required. Such events may require further investigation in order to characterize and understand them. Adverse events of special interest may be added, modified or removed during a study by protocol amendment.

- Pregnancy occurring in a female participant entered in the clinical trial. It will be qualified as an SAE only if it fulfills one of the seriousness criteria (see Appendix 3 [[Section 10.3](#)]).
 - In the event of pregnancy in a female participant, IMP should be discontinued.
 - Follow-up of the pregnancy in a female participant is mandatory until the outcome has been determined (See Appendix 4 [[Section 10.4](#)]).

- Symptomatic overdose (serious or nonserious) with IMP.
 - An overdose (accidental or intentional) with the IMP is an event suspected by the Investigator or spontaneously notified by the participant (not based on systematic pills count) and defined as at least twice the intended dose within the intended therapeutic interval, adjusted according to the tested drug.
 - Of note, asymptomatic overdose has to be reported as a standard AE.
- Increase in alanine transaminase (ALT) \geq Grade 2.
 - Liver function tests should be performed in patients with onset of otherwise unexplained nausea, jaundice, right upper abdominal pain, fever, or rash. LFTs include AST, ALT, ALP (isoenzymes if increase in ALP \geq Grade 3), total bilirubin (direct bilirubin if total bilirubin $>2 \times$ ULN), GGT, and INR (if total bilirubin $>2.5 \times$ ULN).
 - Discontinue study intervention in case of increase in ALT \geq Grade 2 if still on treatment, and repeat Liver function tests (LFTs) within 2-3 days. If not recovered, monitor LFTs weekly until recovery to Grade ≤ 1 (or baseline grade). Confounding factors such as, hepato-biliary disorders, concomitant medications, etc. should be excluded prior to study treatment discontinuation.
 - An ultrasound or other imaging in liver should be considered based on the clinical presentation.
 - A consultation with a hepatologist should be undertaken if there is,
 - unexplained or persistent increase in ALT \geq Grade 3 despite study treatment discontinuation.

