9.4.2.2 Analyses of clinical laboratory evaluations

Hematology and clinical chemistry results will be graded according to the NCI-CTCAE v5.0, when applicable. Number and percentage of participants with laboratory abnormalities (ie, all grades and by grade) using the worst grade during the on-treatment period will be provided for the safety population.

When the NCI-CTCAE v5.0 grading scale is not applicable, the number of participants with laboratory abnormality out-of-normal laboratory range value will be displayed.

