2.1.4 Safety endpoints

The safety analysis will be based on the reported adverse events (AEs) and other safety information, such as clinical laboratory data, vital signs, weight, electrocardiogram (ECG) and ECOG PS.

Observation period

The observation period starts from the time when the patient gives informed consent and is divided into 3 periods:

- The pre-treatment period is defined as the time from when the participants give informed consent to the first administration of the IMP.
- The on-treatment period is defined as the time from the first dose of IMP up to last dose of IMP.
- The post-treatment safety follow-up period is defined as the time from last administration of the IMP to the last administration of the IMP +30 day

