2.1.4.3 Laboratory safety variables

Clinical laboratory data consists of blood analysis including hematology and biochemistry. Clinical laboratory values will be converted into standard international units that will be used in all listings and tables.

For laboratory safety variables, parameters measured on the day of the first study treatment intake will be considered as part of the baseline measurements.

For laboratory safety variables, the treatment period will start at first study treatment intake +1 day.

The laboratory safety parameters will be classified as follows:

- Hematology
 - **Red blood cells, platelets, and white blood cells:** platelet count, red blood cell (RBC) count, hemoglobin, hematocrit, white blood cell with differential: neutrophils, lymphocytes, monocytes, eosinophils, and basophils.
 - **Coagulation:** prothrombin time (PT) and international normalized ratio (INR).
- Biochemistry
 - **Metabolism:** fasting glucose, total protein.
 - **Electrolytes:** potassium, sodium, calcium.
 - **Renal function:** creatinine, blood urea nitrogen (BUN), urea, eGFR
 - **Liver parameters:** alanine aminotransferase (ALT), aspartate aminotransferase (AST), alkaline phosphatase, total and direct bilirubin.
- Hormone:
 - **Follicle-stimulating hormone** (for women with non-childbearing potential)

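### Laboratory shift and PCSA tables and the protocol's worst-grade table end at the last dose, so an early stopper's Day 14 panel and later liver tests are not counted in them

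*SAP*

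**What the plan says.** **Window.** SAP 2.1.4: "The on-treatment period is defined as the time from the first dose of IMP up to last dose of IMP". SAP 2.1.4.3 changes only the start for laboratory data: "For laboratory safety variables, the treatment period will start at first study treatment intake +1 day". It gives no separate end.

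**Tables.**
- Shift tables (SAP 2.4.6.3): "shift tables showing the number of patients in each grade at baseline by grade during the on-treatment period will be provided". Laboratory PCSA incidence has the same limit.
- Worst-grade table in Protocol 9.4.2.2: "using the worst grade during the on-treatment period will be provided for the safety population".
- Grade table in SAP 2.4.6.3: "The frequency of patients in each grade and all grades of laboratory abnormalities during treatment will be summarized". The protocol synopsis refers to the treatment period. Neither is tied to the defined on-treatment period.
- Low/normal/high table in SAP 2.4.6.3, for tests with neither CTCAE nor PCSA criteria: no window stated.
- Percentages of laboratory abnormalities are based on participants with at least one evaluation of the test in the period considered.

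**Collection.** The schedule (Protocol 1.3) places the laboratory row, "Standard hematology, clinical chemistry and coagulation panels", at screening, at Day 1 as a conditional repeat, and at Day 14. There is no Day 7 panel. For participants who stop early, Protocol 7.1.1 says: "All procedures pre-scheduled for these Day 7 and Day 14 visits will be performed except PK sampling and ECG". After a stop for raised ALT, Protocol 8.3 says to "repeat Liver function tests (LFTs) within 2-3 days", followed by weekly tests if not recovered. Protocol 8.2.4 has Grade 3 or higher liver tests repeated, including those found within 30 days after the last dose.

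**The concern.** Laboratory abnormalities are part of the secondary safety endpoint and are compared descriptively by arm. The tables above leave out values from participants who stopped early. Some of them will have stopped for toxicity, since Protocol 6.6 and 8.3 link Grade 3 or higher events and ALT of Grade 2 or higher to discontinuation. The omitted values may therefore differ systematically from those shown. The same SAP runs every TEAE table in two windows, the second to last dose +30 days, but gives laboratory data only one.

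Two neighbouring safety rules have similar faults.
- **Vital-sign PCSA (SAP 2.4.6.4).** The numerator counts participants with an event in the on-treatment period. The denominator counts participants assessed in the TEAE period, which has two definitions.
- **TEAEs and dosing.** Protocol 9.4.2.1 plans a table of TEAEs leading to dose modification. SAP 2.4.6.1 tabulates only those leading to dose reduction, although Protocol 6.6 speaks of omission and discontinuation and SAP 2.4.4 counts omission as a modification. SAP 1.6 does not record the narrowing.

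**Working it through.** The plan gives no figure to reproduce. The check is a day count followed by a sensitivity calculation on assumed counts.

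**Day count, using the protocol's own example of a stop on Day 6 (Protocol 7.1.1)**
1. Laboratory window: Day 2 (first intake +1 day) to the last dose, at the latest Day 6.
2. Only scheduled post-baseline panel: Day 14, which is 14 − 6 = 8 days after the window closes.
3. A repeat liver test 2 to 3 days after stopping falls on about Day 8 or 9, also outside, as do all weekly tests.
4. SAP 2.5.4 admits unscheduled values to worst grades but does not lengthen the period. Without an unscheduled test while on drug she has no value in the window and leaves the denominator.
5. A participant who completes treatment is unaffected for her Day 14 panel: the Day 14 dose is taken on site after the pre-dose assessments (Protocol 1.3 and 8).

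**Tests affected.** Laboratory PCSA criteria (SAP Appendix H) cover BUN, chloride, basophils, monocytes, RBC and hematocrit. The liver tests are therefore a matter for the grade and shift tables. The low/normal/high table excludes CTCAE-gradable tests such as ALT.

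**Size.** The documents give no early-stopping rate. Two weak proxies are the 1% in earlier window trials who could not have surgery because of adverse events (Protocol 2.1) and the 5% allowed as non-evaluable (Protocol 9.2). With n = 42 per arm, 0.01 × 42 = 0.42 and 0.05 × 42 = 2.1 participants. A wider assumption of 10% gives 4.2.

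Let k be the participants with no value in the window and m the in-window cases (both assumed).
- Shown: m/(n − k).
- With later values counted: from m/n (all k normal) to (m + k)/n (all k abnormal on that test).

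| k | Shown, m = 3 | Later values counted, m = 3 | Shown, m = 0 | Later values counted, m = 0 |
|---|---|---|---|---|
| 0 | 3/42 = 7.1% | 7.1% | 0% | 0% |
| 1 | 3/41 = 7.3% | 3/42 to 4/42 = 7.1% to 9.5% | 0% | 0 to 1/42 = 0% to 2.4% |
| 2 | 3/40 = 7.5% | 3/42 to 5/42 = 7.1% to 11.9% | 0% | 0 to 2/42 = 0% to 4.8% |
| 4 | 3/38 = 7.9% | 3/42 to 7/42 = 7.1% to 16.7% | 0% | 0 to 4/42 = 0% to 9.5% |

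Enrolment ended early. At an assumed n = 30 and m = 0, the upper ends are 1/30 = 3.3% (k = 1) and 2/30 = 6.7% (k = 2).

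**Vital-sign PCSA.** If the TEAE period is read as first to last dose, numerator and denominator agree. If it is read as last dose +30 days, a participant measured only after her last dose enters the denominator but can never enter the numerator. SAP 2.1.4.4 separately calls a participant evaluable only if she has an on-treatment measurement, so the sections conflict under that reading.

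**The case against.** The case on the other side is substantial.

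- **An on-treatment window is a legitimate, prespecified choice.** A panel 8 days after the last dose is 192 h later, or 192/20 = 9.6 half-lives at the roughly 20 h given in Protocol 4.3 (preliminary single-dose data), so it says little about toxicity on drug. Surgery follows on Day 15 (+1) and no later panel is scheduled, so a +30-day table would hold for-cause and post-surgical values for those who complete treatment. This stands. It is why the on-treatment tables should stay and any added set be labelled.
- **The values are not lost to all reporting.** A reader might infer that they enter no laboratory summary. The documents do not support that. The schedule labels the 14 days as the treatment period, so on one reading of the SAP grade table a stopper's Day 14 panel counts. Protocol 9.4.2.2 points the other way, which makes this an ambiguity. The low/normal/high table has no window at all. ALT of Grade 2 or higher is listed as an AESI with day of occurrence and outcome (SAP 2.1.4.1 and 2.4.6.1), though laboratory grade is not among the listing's stated contents. Abnormalities that qualify as adverse events reach the TEAE tables to last dose +30 days.
- **Missing counts are not wholly absent.** A reader might infer that none are planned. SAP 2.5.3 presents them where relevant, and the denominators, if printed, reveal the shortfall. Neither commits to a count per test and arm.
- **The loss is less informative than it looks for liver tests.** A value that triggers a stop while on treatment stays in the worst-grade and shift tables. What drops out for that participant is a later peak or the recovery.
- **Letrozole reductions.** With one tablet a day, a reader might infer that this arm can have none. SAP 2.4.4 defines a reduction against the previous day or the day before an omission. A participant who takes an extra tablet, skips the next day and resumes one tablet meets that definition. The case is unusual, but the category is not empty by construction.

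**Conclusion.** The point holds for the shift tables, the laboratory PCSA table and the protocol's worst-grade table. As defined, they exclude everything after the last dose, and an early stopper without an unscheduled on-treatment test disappears from their denominators. For the SAP grade table and the low/normal/high table the defect is an unstated end of window, not a demonstrated exclusion.

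Each affected participant is 1/42 = 2.4 percentage points at the planned arm size, and more in the smaller arms left by early termination. The number affected is unknown and probably small. The ranges above rest on assumed k, m and n, and their upper ends need every stopper to be abnormal on the same test. The primary endpoint is untouched, and the consequence is limited to how completely a descriptive secondary safety endpoint is reported.

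The vital-sign PCSA percentage is inconsistent under one of the two TEAE definitions, and the dose-reduction table is narrower than the protocol's plan. Both need correcting whatever the number of early stoppers. The ECG analysis, called on-treatment but using the TEAE period, is a lesser inconsistency, because ECGs are not performed at the planned visits after an early stop.

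**What to change.** 1. State one end of window for all on-treatment laboratory tables in SAP 2.4.6.3, including the grade and low/normal/high tables, and align the grade table with Protocol 9.4.2.2.
2. Keep the on-treatment tables. Add a parallel set of grade, shift and PCSA tables from first dose to last dose +30 days, matching the second TEAE window.
3. In both sets show the number assessed per test and arm. In the added set show the Day 14 visit result separately, and note that values after Day 14 are for-cause or post-surgical.
4. Use the same window for the numerator and denominator of vital-sign PCSA; the on-treatment period would agree with SAP 2.1.4.4.
5. Replace the dose-reduction table with TEAEs leading to dose modification, using the SAP 2.4.4 definition (reduction or omission), as Protocol 9.4.2.1 plans.
6. Record these changes in SAP 1.6.

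The cost is SAP wording and one further set of laboratory tables, with no new data collection, provided the repeat liver tests are entered in the eCRF. The drawback is selective ascertainment after Day 14, which the labelling, the separate Day 14 display and the retained on-treatment tables make visible but do not remove.

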9.4.2 Safety analyses

All safety analyses will be performed on the Safety Population.

Table 6 - Safety analyses

Endpoint	Statistical Analysis Methods
Primary	No primary endpoint is defined for safety analyses
Secondary	
AEs/SAEs and laboratory abnormalities	Descriptive statistics
Exploratory	Will be described in the statistical analysis plan finalized before database lock

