10.2 APPENDIX 2: CLINICAL LABORATORY TESTS

The tests detailed in [Table 7](#) will be performed by the local laboratory.

- Protocol-specific requirements for inclusion or exclusion of participants are detailed in [Section 5](#) of the protocol.
- Additional tests may be performed at any time during the study as determined necessary by the Investigator or required by local regulations.

Table 7 - Protocol-required laboratory assessments

Laboratory assessments	Parameters
Hematology	Platelet count Red blood cell (RBC) count Hemoglobin Hematocrit White blood cell (WBC) count with differential: Neutrophils Lymphocytes Monocytes Eosinophils Basophils
Clinical chemistry	Blood urea nitrogen (BUN) or urea Creatinine Glucose fasting Potassium Sodium Calcium Aspartate aminotransferase (AST)/Serum glutamic-oxaloacetic transaminase (SGOT) Alanine aminotransferase (ALT)/Serum glutamic-pyruvic transaminase (SGPT) Alkaline phosphatase Total and direct bilirubin Total protein
Coagulation	Prothrombin time International normalized ratio (INR)
Other screening tests	Follicle-stimulating hormone (as needed to confirm postmenopausal status) Viral serologies including hepatitis A antigen or IgM hepatitis A antibody, HBs antigen or hepatitis B viral DNA, hepatitis C antibody or quantitative hepatitis C viral (HCV) ribonucleic acid (RNA) The results of each test must be entered into the CRF

Investigators must document their review of each laboratory safety report.

10.3 APPENDIX 3: ADVERSE EVENTS: DEFINITIONS AND PROCEDURES FOR RECORDING, EVALUATING, FOLLOW-UP, AND REPORTING

DEFINITION OF AE

AE definition

- An AE is any untoward medical occurrence in a patient or clinical study participant, temporally associated with the use of study intervention, whether or not considered related to the study intervention.

NOTE: An AE can therefore be any unfavorable and unintended sign (including an abnormal laboratory finding), symptom, or disease (new or exacerbated) temporally associated with the use of study intervention.

Events meeting the AE definition

- Any abnormal laboratory test results (hematology or clinical chemistry) or other safety assessments (eg, ECG, radiological scans, vital signs measurements), including those that worsen from baseline, considered clinically significant in the medical and scientific judgment of the Investigator (ie, not related to progression of underlying disease), eg:
 - Leading to IMP discontinuation or modification of dosing, and/or

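### For the few collected laboratory tests that have a PCSA criterion but no CTCAE grade, the SAP replaces the protocol's out-of-range count with PCSA incidence, so some out-of-range values reach no specified table

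*SAP*

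**What the plan says.** Protocol 9.4.2 lists "AEs/SAEs and laboratory abnormalities" as a secondary safety endpoint, analysed descriptively. For tests that CTCAE v5.0 cannot grade, protocol 9.4.2.2 has a single rule: "the number of participants with laboratory abnormality out-of-normal laboratory range value will be displayed".

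SAP 2.4.6.3 divides those tests into two groups.

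- Tests with a PCSA criterion in Appendix H. The section opens this group with "For laboratory tests for which NCI-CTCAE V5.0 scale is not applicable, potentially clinically significant abnormalities (PCSA) values are defined as abnormal values" judged medically important against preset thresholds. The output is: "The incidence of PCSA any time during the on-treatment period will be summarized by treatment group irrespective of the baseline level".
- Tests with neither a grade nor a PCSA criterion, which are sorted against normal ranges: "Laboratory parameters for which both CTCAE grading or PCSA criteria are not applicable will be classified into low/normal/high group". The planned output in this second group reads: "a summary table which present the frequency of patients with any abnormal test will be provided".

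Only the second group keeps the protocol's rule.

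Appendix H has laboratory criteria for six tests: BUN, chloride, basophils, monocytes, RBC and hematocrit. Chloride is not among the required tests in protocol Table 7, so five collected tests are involved. Table 7 also lets a site report "Blood urea nitrogen (BUN) or urea".

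**The concern.** For the PCSA tests, the SAP's count takes the place of the protocol's count. If a PCSA limit lies beyond the normal range, a participant whose value falls between the two is abnormal under the protocol and uncounted under the SAP. If a test has no PCSA limit on the low side, every low value is uncounted.

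Nothing else in SAP 2.4.6.3 fills the gap. Its shift tables are by CTCAE grade, so they omit ungraded tests. It specifies no summary of laboratory values or of change from baseline, although SAP 2.4.6.4 and 2.4.6.5 specify summaries by visit or time point for vital signs and ECG. The general convention for continuous data in SAP 2.4 names no laboratory table.

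At stake is a modest part of the secondary safety endpoint. A moderate shift in one of these tests could go untabulated, and a statistician following the protocol would report different counts from one following the SAP.

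**Working it through.** The documents state no figure to reproduce, so the check sets the SAP's two appendices side by side.

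**Inputs.** Normal ranges are from SAP Appendix F, Tables 5 and 6, using the female range where it is sex-specific because the trial enrols women only. PCSA limits are from SAP Appendix H. The ratio is the high PCSA limit divided by the upper limit of the range.

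| Test | Appendix F range | Appendix H PCSA | Ratio | Out of range but uncounted |
|---|---|---|---|---|
| BUN (mmol/L) | 3.6–7.1 | ≥17 | 17/7.1 = 2.39 | >7.1 to <17; <3.6 |
| Monocytes (10⁹/L) | 0.18–0.5 | >0.7 | 0.7/0.5 = 1.40 | >0.5 to 0.7; <0.18 |
| RBC, female (10¹²/L) | 4–5.2 | ≥6 | 6/5.2 = 1.15 | >5.2 to <6; <4 |
| Hematocrit, female (v/v) | 0.36–0.46 | ≤0.32 or ≥0.50 | 0.50/0.46 = 1.09 | >0.46 to <0.50; >0.32 to <0.36 |
| Basophils (10⁹/L) | 0–0.15 | >0.1 | 0.1/0.15 = 0.67 | none |

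**High side.** Four of the five collected tests have a band of high values that the PCSA rule misses. It is wide for BUN, moderate for monocytes, and narrow for RBC and hematocrit.

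**Low side.** BUN, monocytes and RBC have no low PCSA limit, so all their low values are missed. Hematocrit has a low limit, but values above 0.32 and below 0.36 are missed.

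**Basophils.** The mismatch runs the other way. Values above 0.1 and up to 0.15 are inside the Appendix F range, yet they count as PCSAs.

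**BUN and urea.** SAP 2.1.4.3 names both under renal function, and Appendix F gives both 3.6–7.1 mmol/L. Appendix H has a row for BUN and none for urea. Take a result of 10 mmol/L:

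- Labelled urea, it has no PCSA criterion, so it falls to the low/normal/high rule. Since 10 > 7.1, it is counted as high.
- Labelled BUN, it falls to the PCSA rule. Since 10 < 17, it is not counted.

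The same number is therefore treated differently according to the label the site reports.

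**The case against.** **The protocol text is only a summary.** Protocol 9.4 says so, and the SAP may refine it. The SAP may indeed add detail. Here, though, it omits a stated output for certain tests rather than elaborating it.

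**The consequences are small.** This stands. Tests with CTCAE grades, including the liver enzymes, keep their grade and shift tables. Hemoglobin has a generic range used for grading, and creatinine and eGFR are collected. Results that the investigator judges clinically significant are reported as adverse events under protocol Appendix 3. The primary endpoint and the adverse events of special interest are untouched.

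**The BUN/urea split may be unintended.** The SAP nowhere says that urea is exempt from the BUN criterion, and a programmer might apply it to both. That is a fair guess at intent, but the text as written does not say it.

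**Appendix H may be incomplete as read.** SAP 2.5.3 uses an eosinophil PCSA as an example, yet the appendix shows no eosinophil row, and a figure is missing there. Further rows could change which tests are affected, and a urea row would remove the BUN/urea split.

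**Stronger readings to avoid.** A reader might infer any of the following, and the documents do not support them.

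- That the SAP counts only extreme values for all ungraded tests. Tests without a PCSA criterion keep the normal-range count, the basophil limit is stricter than the range, and only BUN has a far more extreme limit.
- That silence in SAP 1.6 shows an undisclosed change. That table records major changes made in the amended SAP. It is not a full log of differences from the protocol.
- That a number of missed patients per arm can be given. The documents give no distribution for these tests, and SAP 2.4 says that the planned sample size will not be reached.

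**Conclusion.** The point holds in a narrow form and is minor. For BUN, monocytes, RBC and hematocrit, values that are out of range but short of the PCSA limit enter no specified laboratory table, although protocol 9.4.2.2 promises to display them. For basophils, Appendices F and H disagree in the opposite direction. BUN and urea are counted by different rules despite sharing a unit and range.

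This rests on two assumptions. First, the Appendix F generic ranges stand in for the normal ranges that the protocol means. Tests are run locally, and local ranges would move the edges of each gap. Second, the Appendix H laboratory tests are taken as ungraded, because SAP 2.4.6.3 defines laboratory PCSAs for such tests. Neither document lists which tests lack a CTCAE grade.

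**What to change.** In SAP 2.4.6.3:

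1. Extend the low/normal/high classification and its table to every laboratory test without a CTCAE grade, whether or not Appendix H has a criterion for it. Keep PCSA incidence beside it as an addition.
2. Apply one rule to BUN and urea, either by treating them as one parameter or by giving both the same Appendix H criterion.
3. Reconcile the basophil limits in Appendices F and H, or explain why the PCSA limit is set inside the range.
4. State whether generic or local ranges define low, normal and high for these tests.

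The cost is a few sentences in the SAP and a few rows in a descriptive safety table. No new data are needed.
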